**Table 15.2.1 2: Full Analysis Set- CCQ score**

CCQ		N	Mean	CI 95%	Std	Min	Median	Max	Nmiss
CCQ score									
Baseline (Visit 1)	Symptom								
	Functional state (CCQ-4)								
	Mental state								
	Total CCQ score								
Week 6 (appr.) (Visit 2)	Symptom								
	Functional state (CCQ-4)								
	Mental state								
	Total CCQ score								

Secondary endpoints

**Table 15.2.1 3: Full Analysis Set- Absolut change of CCQ score between baseline and week 6 (approximately)**

CCQ	N	Mean	CI 95%	Std	Min	Median	Max	Nmiss
CCQ score- Change between baseline and Week 6 (approximately)								
Symptom								
Functional state (CCQ-4)								
Mental state								
Total CCQ score								

**Table 15.2.1 4: Full Analysis Set- General condition of the patient evaluated by the physician (PGE- score)**

General condition of patient (PGE score)*		N	%
anamnesis_general_condition	1		
Baseline (Visit 1)	2		
	3		
	4		
	5		
	6		
	7		
	8		
	Missing		
	Number of patients		
	visit_general_condition	1	
Week 6 (approximately) (Visit 2)	2		
	3		
	4		
	5		
	6		
	7		
	8		
	Missing/Not applicable		
	Number of patients		

\*poor=1-2, satisfactory=3-4, good=5-6, excellent=7-8

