9.4 DATA SOURCES

Medical records collected through routine clinical care will be used to assess the inclusion/exclusion criteria of patients. Such medical records will be used for patient demographics, smoking history, collection of previous COPD medication, concomitant diseases, and concomitant medication.

All patients will be enrolled consecutively.

The treating physician will use the Physician's Global Evaluation (PGE) to evaluate the general condition of the patient on an 8-point ordinal scale from 1 (very poor) to 8 (excellent). PGE will be completed before and approx. 6 weeks after treatment initiation. The modified Medical Research Council (mMRC) scale will be used to assess the breathlessness state of the patient before the treatment. The mMRC stage (0 to 4) collected from the patient as well as the exacerbation history will be used to automatically calculate the GOLD patient group (B, C, or D) in the eCRF.

The CCQ questionnaire contains 10 questions about everyday physical activity and functioning. Each question can be scored by patients on a 7-point scale between 0 and 6. The sum of the scores divided by 10 gives the CCQ score, which measures the health and functional status. For the functional status calculation the sum of the 4 questions (# 7, 8, 9, 10) is divided by 4. A change of 0.4 points is considered to be the MCID. This questionnaire will be filled out by the patient and entered into the database. Patients will be asked to complete the CCQ in order to evaluate their health and functional status before and after treatment with Spiolto[®] Respimat[®].

A patient satisfaction survey will also be completed at visit 2, using a 7-point ordinal scale with divisions from very dissatisfied to very satisfied.

Willingness to continue treatment is assessed by a yes/no question.

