9.7 DATA ANALYSIS

Planned analyses

More details will be described in the statistical analysis plan (SAP).

No formal hypothesis testing will be performed since this is a self-controlled study.

All patients who have received at least one dose of Spiolto[®] Respimat[®] will be included in the analysis; this is the treated set. All analyses will be performed on the treated set (as-treated analysis). If patients have missing values for an outcome, those patients will be excluded for that outcome's analysis. For example, if a patient is missing the CCQ score at Visit 1 and/ or Visit 2, that patient will be excluded from the analyses for the primary endpoint of therapeutic success and the secondary endpoint of change in CCQs from Visit 1 to Visit 2.

The assessment will be carried out using SAS[®] software. The statistical characteristics presented in the end-of-text tables will be N / mean / SD / min / median / max for continuous

variables. Tabulations of relative and absolute frequencies will be presented for categorical variables. Incidence rates and 95% CI will be given when appropriate.

The analyses will relate to the following data:

- Patient demographics (gender, age, height, weight)
- Comorbidities (main diagnosis and concurrent diagnosis according to MedDRA, version valid as at the time of database closure)
- COPD related and other concomitant medication (according to the WHO classification, version valid at the time of database closure)
- History of smoking
- Reported exacerbations
- Breathlessness based on mMRC score at visit 1
- Therapeutic success based on CCQ score; primary outcome
- Changes from Visit1 to Visit 2 in the CCQ and CCQ-4 score; secondary outcome
- Patient satisfaction with Spiolto[®] Respimat[®] at visit 2 only; secondary outcome
- General condition of the patient: evaluated by the physician (Physician's Global Evaluation (PGE)), secondary outcome
- Willingness to continue; secondary outcome
- Adverse Drug Reactions (ADR & SADR), fatal AEs, pregnancies
- GOLD spirometric classifications (1, 2, 3, 4) and GOLD patient groups (B, C, D)
- Details of treatment with inhaled respiratory agents before the study
- Details of treatment with respiratory agents during the study
- Reasons for ending treatment during the observation period
- Details of treatment continuation / discontinuation

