**Table 15.2.1 5: Full Analysis Set- Patient satisfaction with Spiolto® Respimat®**

Patient satisfaction		N	%
visit_satisfaction_spiolto	Very satisfied		
Patient overall satisfaction with Spiolto® Respimat® treatment	Satisfied		
	Rather satisfied		
	Neither satisfied nor dissatisfied		
	Rather dissatisfied		
	Dissatisfied		
	Very dissatisfied		
	Not answered		
	Missing		
	Total		
visit_satisfaction_inhalator	Very satisfied		
Patient satisfaction with inhaling from the Respimat® device	Satisfied		
	Rather satisfied		

Patient satisfaction		N	%
	Neither satisfied nor dissatisfied		
	Rather dissatisfied		
	Dissatisfied		
	Very dissatisfied		
	Not answered		
	Missing		
	Total		
visit.satisfaction_handling	Very satisfied		
Patient satisfaction with handling of the Respimat® inhalation device	Satisfied		
	Rather satisfied		
	Neither satisfied nor dissatisfied		
	Rather dissatisfied		
	Dissatisfied		
	Very dissatisfied		
	Not answered		
	Missing		
	Total		

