**Subgroup analysis- Table 6: Analysis stratified by subgroup- Full Analysis Set- General condition of patient (PGE score)**

General condition of patient (PGE score)		Group 1		Group ...		Total	
		N	%	N	%	N	%
anamnesis_general_condition	1						
Baseline (Visit 1)	2						
	3						
	4						
	5						
	6						
	7						
	8						
	Missing						
	Number of patients						
	visit_general_condition	1					
Week 6 (approximately) (Visit 2)	2						
	3						
	4						

General condition of patient (PGE score)		Group 1		Group ...		Total	
		N	%	N	%	N	%
	5						
	6						
	7						
	8						
	Missing						
	Number of patients						

\*bad=1-2, satisfactory=3-4, good=5-6, excellent=7-8

**Subgroup analysis- Table 7: Analysis stratified by subgroup- Full Analysis Set- General condition of patient (PGE score)-  $\chi^2$ -Test**

PGE- $\chi^2$ -Test*	p-Value
Baseline- Group 1 vs. Group ...	
Week 6 (approximately) - Group 1 vs. Group ...	

\*If  $\chi^2$ -Test is not valid, Fisher's Exact test will be done or PGE will be treated as continuous variable and compared by Wilcoxon Rank-Sum Test (Mann-Whitney-U-Test)/Kruskal-Wallis Test.

**Subgroup analysis- Table 8: Analysis stratified by subgroup- Full Analysis Set- Patient satisfaction with Spiolto® Respimat®**

Patient satisfaction		Group 1		Group ...		Total	
		N	%	N	%	N	%
visit.satisfaction_spiolto	Very satisfied						
Patient overall satisfaction with Spiolto ® Respimat ® treatment	Satisfied						
	Rather satisfied						
	Neither satisfied nor dissatisfied						
	Rather dissatisfied						
	Dissatisfied						
	Very dissatisfied						
	Not answered						
	Missing						
	Total						
visit.satisfaction_inhalator	Very satisfied						
Patient satisfaction with inhaling from the Respimat ® device	Satisfied						
	Rather satisfied						
	Neither satisfied nor dissatisfied						
	Rather dissatisfied						
	Dissatisfied						
	Very dissatisfied						
	Not answered						
	Missing						
	Total						
visit.satisfaction_handling	Very satisfied						
Patient satisfaction with	Satisfied						

Patient satisfaction		Group 1		Group ...		Total	
		N	%	N	%	N	%
handling of the Respimat ® inhalation device	Rather satisfied						
	Neither satisfied nor dissatisfied						
	Rather dissatisfied						
	Dissatisfied						
	Very dissatisfied						
	Not answered						
	Missing						
	Total						

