**Subgroup analysis- Table 9: Analysis stratified by subgroup- Full Analysis Set- Patient satisfaction with Spiolto® Respimat® -  $\chi^2$ -Test**

Satisfaction assessment- $\chi^2$ -Test*	p-Value
Patient overall satisfaction with Spiolto ® Respimat ® therapy- Group 1 vs. Group ...	
Patient satisfaction with inhalation device Respimat ® - Group 1 vs. Group ...	
Patient satisfaction with handling of the inhalation device- Group 1 vs. Group ...	

\*If  $\chi^2$ -Test is not valid, Fisher's Exact test will be done or satisfaction will be treated as continuous variable and compared by Wilcoxon Rank-Sum Test (Mann-Whitney-U-Test)/Kruskal-Wallis Test.

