**Listing 15: Full Analysis Set- Secondary endpoints**

org. name; org.city	patient. no	anamnesis. general_condition	visit.general_condition	visit.satisfaction_spiolto	visit.satisfaction_inhalator	visit.satisfaction_handling
Site	Patient-No.	Baseline- PGE score	Week 6 (appr.)- PGE score	Patient overall satisfaction with Spiolto® Respimat® treatment	Patient satisfaction with inhaling from the Respimat® device	Patient satisfaction with handling of the Respimat® inhalation device

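### PGE and patient satisfaction are reported only on a Full Analysis Set that appears to need a total CCQ at both visits, while protocol 9.7 asks for the Treated Set with exclusion outcome by outcome

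*SAP*

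**What the plan says.** **Protocol.** Section 9.7 defines the Treated Set as everyone who took at least one dose. It continues: "All analyses will be performed on the treated set (as-treated analysis". On missing data it says: "If patients have missing values for an outcome, those patients will be excluded for that outcome's analysis". Its example is a patient without a CCQ score at one or both visits, who drops out of therapeutic success and CCQ change. Section 9.3.2.2 names as secondary outcomes the change in CCQ and in CCQ-4, PGE at both visits, satisfaction at Visit 2 and willingness to continue. On the timing of PGE, section 9.4 says: "PGE will be completed before and approx. 6 weeks after treatment initiation". The protocol has no Full Analysis Set (FAS).

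**SAP.** These displays are on the FAS:
- the PGE display (Table 15.2.1 4), titled "Full Analysis Set- General condition of the patient evaluated by the physician (PGE- score"
- the satisfaction display (Table 15.2.1 5), titled "Full Analysis Set- Patient satisfaction with Spiolto"
- Subgroup Tables 6 and 7: "Full Analysis Set- General condition of patient (PGE score"
- Subgroup Tables 8 and 9: "Analysis stratified by subgroup- Full Analysis Set- Patient satisfaction with Spiolto"
- Listing 15: "Full Analysis Set- Secondary endpoints"

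The section headed as the definition of analysis sets (15.1.3) contains only a table of counts. Table 15.1.1 1 gives four reasons for being outside the FAS: a total CCQ at Visit 1 alone, at Visit 2 alone, at neither visit, or not being in the Treated Set. Under SAP section 1, the total CCQ needs all three subscales. The symptom and functional (CCQ-4) scales each tolerate one blank among four items; the mental scale tolerates none among two.

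**The concern.** The protocol's rule ties exclusion to the outcome being analysed. The SAP appears to tie it to the CCQ for outcomes that do not use the CCQ. PGE is a physician rating and satisfaction is a separate Visit 2 question, so both can be valid when the CCQ total cannot be scored. Two named secondary outcomes, with their subgroup comparisons, would then describe only patients selected on CCQ completeness. Readers would see how many patients were excluded and why (Tables 15.1.1 1 and 15.1.3 1, Listing 2), but not those patients' PGE or satisfaction. The same selection would affect CCQ-4 change, which needs only the functional items.

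**Working it through.** **1. What the FAS is.** The four reasons in Table 15.1.1 1, taken together, leave Treated Set patients with a total CCQ at both visits. Other FAS displays fit this poorly:
- Table 15.2.1 1 has a row for missing success status, and a footnote basing percentages on all patients whether or not the CCQ is available.
- Table 15.2.1 4 allows a not-applicable category at Visit 2 but not at Visit 1.
- Tables 15.2.1 6 and 7 restrict the denominator to patients with Visit 2, and Table 7 lists loss to follow-up and death as reasons.
- Sensitivity Table 1 counts missing values for the interval between visits.

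The disposition reasons are the nearest thing to a definition, so the rest of the check uses them as a conditional reading.

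**2. Who loses data on that reading.** Take a patient who attends Visit 2 and leaves item 3 or item 4 blank at either visit. The mental scale fails, so the total fails, so the patient leaves the FAS. PGE at both visits, satisfaction at Visit 2 and CCQ-4 at both visits may all be valid, yet they leave Tables 15.2.1 3, 4 and 5.

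**3. Whether another display restores them.** The Treated Set displays are Tables 15.1.4 1 to 40, the 15.3 tables, and Listings 3 to 12 and 16 to 18. None shows PGE or satisfaction.

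**4. The plan's own figures (protocol 9.5).** These reproduce. At n = 1170 and 50%, the half-width is 1.96 × √(0.5 × 0.5 / 1170) = 2.87 points, giving 47.1% to 52.9%; 1170 / 0.90 = 1300. At 90%, the half-width is 1.96 × √(0.9 × 0.1 / 1170) = 1.72 points.

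**5. Size at Visit 2.** The blank rate is not in the documents. Assume each mental item is blank with probability q = 0.5% to 2% per visit, and that 1170 patients attend Visit 2. Four answers must be present (two items, two visits). The share m without a total CCQ pair is 1 − (1 − q)⁴ if blanks are independent, or q if they are fully dependent.

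| q | m, independent | of 1170 | m, dependent | of 1170 |
|---|---|---|---|---|
| 0.5% | 1.99% | 23 | 0.5% | 6 |
| 1% | 3.94% | 46 | 1% | 12 |
| 2% | 7.76% | 91 | 2% | 23 |

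The eCRF prompts for missing entries (protocol 9.6 and 9.6.1) would lower m; a wholly missing CCQ would raise it. Let g be the FAS proportion minus the proportion among excluded attenders. The FAS figure then differs from the Treated Set figure by m × g. With g assumed between −20 and +20 points:
- largest m: 0.0776 × (±20) = ±1.55 points
- smallest m: 0.005 × (±20) = ±0.1 point
- no gap: 0

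**6. Baseline PGE of patients without Visit 2.** At the planned 10% drop-out, 1300 × 0.10 = 130 patients have a Visit 1 PGE but no Visit 2, if all 1300 are treated and none of the 10% stands for missing CCQ. Whether leaving them out breaks the protocol depends on how its rule is read, as discussed under the objection.

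**The case against.** **The FAS may be wider than inferred.** Several displays listed in step 1 make more sense if the FAS includes patients without Visit 2 or without a CCQ pair. Some may be template defaults, but they cannot all be dismissed. Part of the SAP was also not available to us, so the statement that the set is undefined covers only the text we have. This stands. A reader might infer that the SAP demonstrably discards valid PGE and satisfaction data. The documents do not support that; they show an undefined set whose most explicit description would have this effect. Either way the SAP needs a definition.

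**Baseline PGE.** A reader might also infer that the plan wrongly drops a tenth or more of baseline PGE values. Protocol 9.3.2.2 lists PGE at Visit 1 and Visit 2 as one outcome, and the example in 9.7 removes a patient who lacks either visit. Applied to PGE, that rule would drop patients without Visit 2 as well. The example concerns a change score, so a per-visit reading is possible, but the text does not settle it. The figure of 130 therefore counts as a departure only on the per-visit reading.

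**Willingness to continue.** Tables 15.2.1 6 and 7 are also on the FAS, but Table 15.1.1 1 and Listing 6 give continuation and the reasons for stopping without a CCQ condition. Nothing is lost there; the risk is two differing figures.

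**CCQ-4.** The protocol's example speaks of change in the CCQ scores generally and could be stretched to cover CCQ-4. However, SAP section 1 gives CCQ-4 its own availability rule, and outcome-by-outcome exclusion points to using it.

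**Small effect.** The shift is entirely assumed, and at its largest it lies below both half-widths in step 4. This limits the importance of the point but does not remove the conflict between the documents.

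**Conclusion.** The conflict between protocol 9.7 and the SAP's set labels for PGE and satisfaction is in the text. On the disposition-table reading of the FAS, Visit 2 attenders without a total CCQ pair lose valid PGE, satisfaction and possibly CCQ-4 change, against the protocol's rule. Under the assumed blank rates that is 6 to 91 of 1170 attenders. It moves a Visit 2 proportion by 0 to about 1.6 points, in an unknown direction. The documents give neither the blank rate nor the gap, and the bias may be zero. The primary estimate is not affected, because the inferred set matches the protocol's own exclusion for total CCQ success. The 130 baseline PGE values add to the departure only if the protocol's rule is read per visit. The point should be corrected in the SAP, but it does not threaten the main result.

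**What to change.** - Run Tables 15.2.1 4 and 5, Subgroup Tables 6 to 9 and Listing 15 on the Treated Set, with availability judged per outcome and N shown.
- For PGE, show the patients rated at both visits, so that the two distributions describe the same people. Add the all-available Visit 1 distribution if the protocol's rule is meant per visit, and say which reading is intended.
- Analyse CCQ-4 change on patients with a calculable CCQ-4 at both visits.
- Keep the total-CCQ-complete set for total CCQ success and change only. Define it in the SAP text and reconcile it with the missing row and footnote of Table 15.2.1 1, the Visit 2 category in Table 15.2.1 4, the denominators and reasons in Tables 15.2.1 6 and 7, and the missing count in Sensitivity Table 1.
- If the FAS is kept for PGE and satisfaction, state and justify the departure from protocol 9.7.

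The cost is changed set flags and table titles, a definition and a paired PGE display; no new data are needed. The downside is that denominators will differ between tables, which is why N must be shown in each.

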9. RESEARCH METHODS

9.1 STUDY DESIGN

This is a self-controlled non-interventional study (NIS), as referred to in §4.23 and §67.6 AMG, enrolling consented COPD patients who will be treated with Spiolto[®] Respimat[®] according to the approved SmPC.

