9.3 VARIABLES

The following parameters will be collected and assessed at visit 1 and/ or visit 2:

- Patient demographics (age, gender, height & weight)
- Smoking status (current smokers, former smokers, and never smokers) and pack-years
- Concomitant diseases / Comorbidities such as cardiovascular disease, diabetes mellitus, musculoskeletal impairment, renal diseases, liver diseases, osteoporosis, gastroesophageal reflux (GERD), or lung cancer
- COPD-related and other concomitant medication such as beta-blockers, beta-agonists, corticosteroids, or proton pump inhibitors
- Reported exacerbations based on medical history in the last 12 months and exacerbations leading to hospitalization in the last 12 months
- Assessment of the severity of breathlessness based on the Modified Medical Research Council Questionnaire (mMRC)
- Health and functional status based on CCQ scores
- Patient satisfaction with Spiolto[®] Respimat[®] to assess the overall satisfaction with Spiolto[®] Respimat[®] as well as specific inhalation from the device and device handling
- General condition of patient based on Physician's Global Evaluation (PGE) to assess the general condition of the patient at the beginning and at the end of the study
- Safety Reporting; Adverse Drug Reactions (serious and non-serious), fatal AEs, and pregnancies at the beginning and at the end of the study
- GOLD spirometric classifications (1, 2, 3, 4) and GOLD patient groups (B, C, D) based on GOLD guidelines 2017

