9.3.2.2 Secondary outcomes

- Changes in the CCQ and CCQ-4 score from visit 1 to visit 2
- General condition of the patient, evaluated by the physician (PGE score) at visit 1 and visit 2.
- Patient satisfaction with Spiolto[®] Respimat[®] at visit 2.
- Willingness to continue treatment with Spiolto[®] Respimat[®] at visit 2 as proxy for adherence

The secondary outcomes are not safety outcomes.

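### The planned PGE tables show each visit separately, so they cannot give how many patients improved, stayed the same or worsened, and the week-6 subgroup test does not address change

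*SAP*

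**What the plan says.** Protocol 9.1 sets the design: "This is a self-controlled non-interventional study (NIS". There is no comparator group, so a patient's own baseline is the only reference. Under Protocol 9.4 the physician is to "evaluate the general condition of the patient on an 8-point ordinal scale from 1 (very poor) to 8 (excellent", and "PGE will be completed before and approx. 6 weeks after treatment initiation". Protocol 9.3 gives the purpose: "to assess the general condition of the patient at the beginning and at the end of the study". Protocol 9.3.2.2 lists the secondary outcome as "General condition of the patient, evaluated by the physician (PGE score) at visit 1 and visit 2". No change score is named there, although the CCQ and CCQ-4 entry in the same list is worded as a change.

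The SAP plans three PGE summaries, all on the Full Analysis Set (FAS):

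- Table 15.2.1 4, "General condition of the patient evaluated by the physician (PGE- score": N and % in each of the eight categories, one block for Visit 1 and one for Visit 2.
- Subgroup Table 6: the same two blocks by subgroup.
- Subgroup Table 7: a chi-square test between subgroups, with Fisher or a rank test as fallback. It has one row for "Baseline- Group 1 vs. Group" and a second for "Week 6 (approximately) - Group 1 vs. Group".

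SAP section 1 derives no PGE change variable. Listing 15 prints the two scores side by side for each patient, with no change column and no summary.

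**The concern.** In a before-after study the informative quantity is what happened within each patient. Two separate frequency distributions show the net movement of the group, but not how many patients moved up, stayed put or moved down. A report built on these tables could say that the distribution shifted upward. It could not say whether few or many patients were rated worse after six weeks, which a clinical reader will want to know.

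The subgroup test has a related weakness. Several of the 13 subgroup sets in SAP 2.5 are defined by severity or disease burden: spirometric stage, GOLD group, exacerbations, hospitalizations and cardiac comorbidity. Baseline PGE may well differ across them. If it does, the groups will tend to differ at week 6 even when they change equally, and the week-6 p-value could be misread as differential benefit.

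**Working it through.** **1. CCQ and PGE in the same SAP**

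| Step | CCQ | PGE |
|---|---|---|
| Change variable derived (section 1) | yes | no |
| Change tabulated overall | Table 15.2.1 3, with 95% CI | no |
| Change tabulated by subgroup | Subgroup Table 4 | no |
| Change compared between subgroups | Subgroup Table 5, rank-based | no; Subgroup Table 7 compares each visit separately |

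The SAP gives no reason for the difference.

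**2. The plan's own figure**

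No figure is stated for PGE. The precision statement in Protocol 9.5 reproduces: with p = 0.50 and n = 1170, 1.96 × √(0.25/1170) = 0.0287, giving 47.1% to 52.9%; and 1170/0.9 = 1300. I use n = 1170 below as an assumed number of patients with both PGE scores.

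**3. What two marginal distributions leave open**

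None of the inputs in this step comes from the documents.

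*Illustrative model.* Bivariate normal scores with means 4.5 (Visit 1) and 5.1 (Visit 2) and SD 1.4 at both visits, rounded and clipped to 1–8. Only the correlation varies, so both blocks of Table 15.2.1 4 would be the same in every row.

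| Correlation | Improved | Unchanged | Worsened | Worsened, of 1170 |
|---|---|---|---|---|
| 0.3 | 52.3% | 22.1% | 25.6% | 300 |
| 0.5 | 52.6% | 25.3% | 22.0% | 258 |
| 0.7 | 53.3% | 30.5% | 16.3% | 190 |
| 0.9 | 55.2% | 39.3% | 5.5% | 64 |

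In this model the planned tables mainly hide the split between unchanged and worsened. The improved share hardly moves.

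*Bounds without a model.* Take Visit 1 frequencies of 4/10/20/26/20/12/6/2% and Visit 2 frequencies of 2/5/12/21/26/20/10/4% (means 4.18 and 4.84). Linear programming over all 8×8 tables with these margins gives an improved share of 20% to 94% and a worsened share of 0% to 59%. The ends are extreme pairings and not forecasts. They show that the margins alone do not settle either share.

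**4. The week-6 subgroup test**

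Suppose group A has mean PGE 4.0 and group B 5.0 at baseline, and both gain 0.6 (assumed). At week 6 the means are 4.6 and 5.6. The week-6 difference is 1.0, equal to the baseline difference; the difference in change is 0.6 − 0.6 = 0. The week-6 row tests the first quantity and not the second.

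**5. What the fix would show**

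Using p ± 1.96 × √(p(1−p)/1170), a worsened share of 5.5% has a 95% CI of 4.2% to 6.8%, and one of 25.6% has 23.1% to 28.1%. Direct counts would separate these cases clearly.

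**The case against.** The best defence is that the SAP delivers what the protocol asks for. The protocol words the CCQ outcome as a change and the PGE outcome as condition at each visit, and Table 15.2.1 4 reports condition at each visit. That stands: this is a choice of analysis that can be improved, and the two documents do not conflict.

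Four stronger readings might be inferred, and the documents support none of them.

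- *The study cannot say who improved.* It can. Both scores are collected and Listing 15 shows them per patient. Only the planned summaries fall short, although a reader would have to count over about a thousand rows to recover the split.
- *The two blocks cover quite different patients because of missing second visits.* The SAP disposition table excludes from the FAS anyone without a total CCQ score at both visits, so most such patients are in neither block. What remains is PGE missing despite a complete CCQ, and each block has a row for missing values.
- *Ignoring the pairing widens the confidence intervals.* The SAP plans no PGE mean, interval or Visit 1 versus Visit 2 test, so no planned analysis treats the visits as independent.
- *The before-after control is lost.* Pairing is kept for the primary endpoint and for every CCQ change analysis.

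It can also be said that Subgroup Table 7 prints the baseline p-value directly above the week-6 one, so an imbalance would be visible. This helps an attentive reader, but two separate p-values still do not amount to a comparison of change.

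Finally, a mean change treats an ordinal scale as interval, and more subgroup p-values would sit badly with Protocol 9.7, which rules out formal hypothesis testing, and with the protocol abstract, which limits subgroup analyses to the primary outcome and CCQ change. Both points stand and shape the fix.

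**Conclusion.** The concern holds for the planned PGE summary tables and subgroup tests. They cannot give the improved/unchanged/worsened split, and the week-6 subgroup p-value can reflect a baseline difference and not change. That conclusion is structural and needs no numerical assumption.

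The size does rest on assumptions. With means of 4.5 and 5.1, SD 1.4 and correlations of 0.3 to 0.9, the worsened share runs from about 26% to 5.5% behind identical tables, and the improved share only from about 52% to 55%. The documents give no PGE mean, SD or correlation.

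The reach is limited to one secondary outcome. It does not touch the primary endpoint, the CCQ analyses or the sample size, and it should not be read as an inconsistency between SAP and protocol. It is worth correcting because the SAP already handles CCQ this way and the data will be in hand.

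**What to change.** 1. For FAS patients with PGE at both visits, add a Visit 1 by Visit 2 shift table (8×8, or 4×4 using the four bands on the PGE form) and state how many patients it covers.
2. From it, report n (%) improved, unchanged and worsened, each with a 95% CI. A median or mean change is optional and only descriptive, since the scale is ordinal.
3. In Subgroup Tables 6 and 7, report within-patient PGE change by subgroup in place of the week-6 comparison, using the rank-based approach of Subgroup Table 5. Label it descriptive, in line with Protocol 9.7. The baseline frequencies can stay beside it, because change on a bounded scale also depends on the starting level.
4. Derive the PGE change variable in SAP section 1 and add a change column to Listing 15.

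The cost is one or two extra tables and some reprogramming of existing ones. No new data, visits or patients are needed, and replacing the week-6 row adds no p-values.
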